2.2 Rationale

In summary, high-dose INH may be useful in the treatment of TB infection commonly considered INH resistant, but its efficacy will likely depend on the dosage and the degree of resistance. In participants infected with TB with isolated *inhA* mutations, **moderate to high-dose INH is likely to be effective**. Participants infected with TB with *katG* mutations **may derive a therapeutic benefit, provided the dose of INH is sufficiently high**.

Genotypic tests that can detect the most common *inhA* and *katG* mutations conferring INH resistance with a short turnaround time directly from sputum have been developed (Hain MTBDRplus), and their use is endorsed by the World Health Organization (WHO) [36, 37]. These tests can quickly identify participants who are likely to benefit from high-dose INH. Hain MTBDRplus also detects mutations associated with RIF resistance.

Another rapid test, Gene Xpert, detects RIF resistance and has become an important tool for diagnosis of MDR-TB. In South Africa and in other settings, sputum of patients is tested first with Gene Xpert; if RIF resistance is detected, then the Hain test is used to

see if there is also INH resistance and confirm MDR-TB. Once MDR-TB is identified, patient sputum is sent for phenotypic drug sensitivity tests for first-line and second-line TB drugs. For those patients who are very ill and require immediate treatment, an empiric MDR regimen is given; for others, therapy is held until Hain results are available, treatment history can be reviewed, and the appropriate treatment can be chosen and made available to the clinic serving the patient (a process that takes at least 1-2 weeks).

Gene Xpert testing that will test for both RIF and INH resistance at the time of diagnosis (and includes testing for *inhA* and *katG* mutations) is currently under development. Thus, information about the type of INH resistance will soon be available at the start of MDR-TB treatment. We believe that patients with MDR-TB with *inhA* mutations can benefit from moderate- to high-dose INH. **It is also likely that many patients with MDR-TB with *katG* mutations can benefit from high-dose INH.** Whether and at which dosage high-dose INH can **overcome INH resistance** conferred by *inhA* or *katG* mutations can be assessed using an EBA study, in which daily quantitative sputum cultures are collected from patients with sputum smear-positive pulmonary TB [38-41].

In this phase IIa EBA study including participants with INH monoresistant-TB and MDR-TB, we propose combining genotypic and phenotypic INH susceptibility testing, population PK, and PDs to determine the relationship between INH AUC/MIC and bactericidal activity. The study will determine whether or not higher-dose INH has a role in the treatment of TB infection with a bacterium resistant to INH, and if it can be used, the study will enable an optimized dosing strategy based on rapid genotypic tests available at the initiation of TB therapy, a novel approach.

3.0 STUDY DESIGN

This is a two-stage, two-step, phase IIa, open-label, randomized clinical trial among adult participants with sputum smear positive pulmonary TB evaluating the EBA of three different doses of INH among participants infected with *M. tuberculosis* with *inhA* mutations (Group 1). In addition, the EBA of INH among participants with *M. tuberculosis* with no genotypic evidence of INH resistance (Group 2) will be determined. Among participants infected with an *M. tuberculosis* strain with *katG* mutations (Group 3), **the EBA of INH at a dose of 15 or 20 mg/kg will be determined. These doses are selected because doses of up to 15-20 mg/kg appear to be safe (in other studies, as well as in the 15 mg/kg dosing cohort in Group 1 in the current trial) and the safety of doses higher than 20 mg/kg has not been established. In addition, upon preliminary assessment of the EBA data in the *inhA* arms, INH demonstrated activity, and this activity appeared to be dose-related.**

No study drug is administered under Step 1. Data collected in Step 1: (a) determine eligibility to Step 2, and (b) allow characterization of INH MICs in three groups (secondary objective). Groups 1, 2, and 3 consist of participants infected with TB with *inhA* mutations, with DS-TB and with TB with *katG* resistance-conferring mutations, respectively.

The study's primary objectives are addressed via Step 2 evaluations. Participants enrolling to Step 2 receive the study drug, INH, which will be given with vitamin B6 ≥ 25 mg daily, by mouth. During both stages, participants in Group 1 who meet Step 2 entry criteria will be randomized to receive 5, 10, or 15 mg/kg of INH daily for 7 days. During Stage 2, participants in Group 2 who meet Step 2 entry criteria will receive 5 mg/kg of INH daily for 7 days. **During Stage 2, participants in Group 3 who meet Step 2 entry criteria will be randomized 1:1 to receive 15 or 20 mg/kg of INH daily for 7 days.** After completion of 7 days of INH alone, participants will be referred to begin standard anti-TB chemotherapy according to South African TB Control Programme Guidelines.

In Stage 1, Group 1 participants who do not meet Step 2 entry criteria, all Group 2 participants and all Group 3 participants will be referred to the South African TB Control Programme for treatment. In Stage 2, Group 1 participants who do not meet Step 2 entry criteria, Group 2 participants who do not meet Step 2 entry criteria, and **Group 3 participants who do not meet Step 2 entry criteria** will be referred to the South African TB Control Programme for treatment.

In Step 2, prior to initiation of treatment, sputum will be collected for quantitative culture on solid medium (for **CFU for Groups 1 and 2 only**) and liquid medium (for determination of **TTD for all groups**) and for MIC determination and phenotypic DST. In addition to GenoType MTBDRplus, GenoType MTBDRsI, which identifies additional mutations associated with resistance to fluoroquinolones **and injectable TB medicines**, will be performed on sputum of participants with MDR-TB (but not INH-monoresistant TB) who are enrolled in the study. Sixteen-hour sputum collections will be performed daily during INH treatment, as per standard EBA methodology [42]. Sampling for PK analysis will be performed at steady state on Day 6 (± 1). NAT2 genotyping will be performed on a blood sample to help explain variability in INH PK parameters, and a saliva sample will be collected for evaluation of a new rapid NAT2 genotyping test. Safety and tolerability will be monitored via clinical evaluations throughout the study and through scheduled laboratory evaluations.

To avoid unnecessary delay in initiating TB treatment, screening evaluations for Step 1 and Step 2 may occur on the same day.

To minimize risk to study staff and study participants, participants with MDR-TB will be hospitalized on a different ward from participants with DS-TB or INH-monoresistant TB. Strict infection control practices will be followed, including the wearing of N95 masks where appropriate and hospitalization on wards with negative pressure ventilation. In addition, persons with a previous known exposure to XDR-TB or those who have been treated previously for MDR-TB, and thus have a higher risk of XDR-TB, will not be included in this study.

The study will proceed in two stages, as follows:

Stage 1—Pilot study to ensure feasibility:

Participants will be recruited at a single clinical site, Task Applied Science at Brooklyn Chest Hospital, affiliated with Stellenbosch University, in Cape Town, South Africa. All eligible participants will enter Step 1 of the study (determination of INH resistance, measurement of INH MIC). Among Group 1 participants who meet the Step 2 entry criteria, 15 participants will be randomized 1:1:1 to receive 5, 10, or 15 mg/kg daily of INH for 7 days with evaluations performed as described above.

As of March 26, 2015, Stage 1 is complete. A total of 15 Group 1, 44 Group 2, and 12 Group 3 participants were enrolled in Step 1 only during Stage 1. These participants did not receive study treatment. They provided sputum samples for MIC determination.

The goal of Stage 1 will be to demonstrate feasibility, not treatment efficacy. The rate at which the study accrues Group 1 participants at a single site will be assessed after 6 months to determine the advisability of proceeding with Stage 2 and advisability of including additional sites. In addition, the standard deviations (SDs) of the primary endpoint will be reviewed for a possible sample size increase if the SDs in Group 1 are larger than expected.

Stage 2:

During Stage 2, to be conducted at Task Applied Science and other approved sites, Group 1 participants who meet Step 2 entry criteria will be randomized 1:1:1 to receive 5, 10, or 15 mg/kg of INH daily for 7 days until the accrual target (taking together participants who enrolled during Stage 1 and Stage 2) is met. Study drug administration and study procedures will be as described above. In addition, 16 Group 2 participants who meet Step 2 entry criteria will be enrolled and will receive INH at a dose of 5 mg/kg daily, and undergo study procedures as described above. **Also, 20 Group 3 participants who meet Step 2 entry criteria will be enrolled and randomized 1:1 to receive INH at a dose of 15 or 20 mg/kg daily, and undergo study procedures as described above.**

A minimum of 16 to a maximum of 70 Group 1 participants, a minimum of 48 to a maximum of 64 Group 2 participants, and **a minimum of 64 to a maximum of 84** Group 3 participants will be enrolled in Step 1 only during Stages 1 and 2 combined. Participants enrolling to Step 1 only will not receive study drug. They will provide sputum samples for MIC determination.

[figure not shown]
[figure not shown]
Figure 3.0-1: Study Design Schematic:**Stage 1:**

Figure 3.0-2: Stage 2:

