Each site should file a copy of this CM with the protocol for reference.

The protocol clarification contained in this memo should be implemented immediately.

The reason for this CM is to clarify the washout period for drugs with anti-TB activity.

The following is a clarification to Protocol A5312, Version 3.0, 08/21/18, titled "The Early Bactericidal Activity of High-Dose or Standard-Dose Isoniazid among Adult Participants with

Isoniazid-Resistant or Drug-Sensitive Tuberculosis." This clarification will be included in the next version of the A5312 protocol if it is amended at a future date.

- Section 4.4.2 (Exclusion Criterion for Step 2) has been revised to read:

Receipt of more than 7 cumulative days of second-line anti-TB drugs (including all drugs with anti-TB activity, except INH, RIF, ethambutol, pyrazinamide, and streptomycin) and/or antibiotics intended for bacterial treatment that may have anti-TB activity, including amoxicillin/clavulanate (Augmentin), linezolid, metronidazole, or drugs from the quinolone class, within the 14 days prior to Step 1 screening sputum collection.

NOTE: In participants who have received 7 days or less of these drugs, the minimum washout period for these drugs is 7 days prior to Step 2 pre-entry sputum collection, regardless of how many cumulative days, up to a maximum of 7 days, the drugs have been taken.

Clarification Memo #1 for:

A5312

The Early Bactericidal Activity of High-Dose or Standard-Dose Isoniazid among Adult Participants with Isoniazid-Resistant or Drug-Sensitive Tuberculosis

NIAID CRMS # 11872

Clarification Memo Date: 12 December 2019

ACTG NETWORK COORDINATING CENTER
Social & Scientific Systems
[name]
[name] 20910-3714
[contact]
[contact]

CLARIFICATION MEMO

DATE: December 12, 2019
TO: ACTG CTU Principal Investigators, CRS Leaders, and CTU/CRS Coordinators
FROM: A5312 Protocol Team
SUBJECT: Clarification Memo #1 for Protocol A5312, Version 3.0

This clarification memo (CM) does not result in a change in the protocol informed consent document. The Division of AIDS does not require you to forward it to your institutional review board (IRB); however, you must follow your IRB's policies and procedures. If IRB review of clarification memos is required at your site, please submit this document for review.

Each site should file a copy of this CM with the protocol for reference.

The protocol clarifications contained in this memo should be implemented immediately.

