NOTE: If a participant’s failure to produce sufficient sputum appears to be due to poor technique rather than low volume of sputum production, this evaluation may be repeated.

4.4 Exclusion Criteria for Step 2

4.4.1 Current treatment with INH or receipt of INH during the 7 days prior to Step 2 entry.

NOTE: Participants who have been started on INH-containing anti-TB treatment and have received this treatment for less than or equal to 2 weeks, but for whom TB drugs have been discontinued because of resistance to INH (with or without resistance to RIF), can participate in the study, but may need to be hospitalized, at the discretion of the investigator, while these drugs wash out; the minimum washout period for these drugs is 7 days.

4.4.2 **Receipt of more than 7 cumulative days of second-line anti-TB drugs (including all drugs with anti-TB activity, except INH, RIF, ethambutol, pyrazinamide, and streptomycin) and/or antibiotics intended for bacterial treatment that may have anti-TB activity, including amoxicillin/clavulanate (Augmentin), linezolid, metronidazole, or drugs from the quinolone class, within the 14 days prior to Step 1 screening sputum collection. The minimum washout period for these drugs is 7 days prior to Step 2 pre-entry sputum collection.**

4.4.3 Known exposure to a person diagnosed with XDR-TB or known personal diagnosis of XDR-TB in the past.

4.4.4 Breastfeeding.

4.4.5 Known allergy/sensitivity to INH.

4.4.6 Karnofsky score <60 or poor general condition where any delay in full TB treatment cannot be tolerated in the opinion of the investigator (at screening).

4.4.7 Any of the following co-morbidities, complications, or underlying medical conditions:

- Known current neurological TB (e.g., TB of the spine, TB meningitis)
- Peripheral neuropathy \geq Grade 2, according to the December 2004 (Clarification, August 2009) Division of AIDS (DAIDS) Toxicity Table, within 14 days prior to entry
- Current or history of epilepsy, defined as seizure disorder requiring current treatment with an antiepileptic medicine or history of any seizures within the prior year

4.4.8 Any condition as determined by physical examination, medical history, laboratory data, or chest x-ray which, in the opinion of the investigator, would interfere with participation in the study.

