4.5 Study Enrollment Procedures

4.5.1 Prior to implementation of this protocol, and any subsequent full version amendments, each site must have the protocol and the protocol consent form(s) approved, as appropriate, by their local institutional review board (IRB)/ethics committee (EC) and any other applicable regulatory entity (RE). Upon receiving final approval, sites will submit all required protocol registration documents to the DAIDS Protocol Registration Office (DAIDS PRO) at the Regulatory Support Center (RSC). The DAIDS PRO will review the submitted protocol registration packet to ensure that all of the required documents have been received. Site-specific informed consent forms (ICFs) will be reviewed and approved by the DAIDS PRO and sites will receive an Initial Registration Notification from the DAIDS PRO that indicates successful completion of the protocol registration process. A copy of the Initial Registration Notification should be retained in the site's regulatory files.

Upon receiving final IRB/EC and any other applicable RE approvals for an amendment, sites should implement the amendment immediately. Sites are required to submit an amendment registration packet to the DAIDS PRO at the RSC. The DAIDS PRO will review the submitted protocol registration packet to ensure that all the required documents have been received. Site-specific ICFs will not be reviewed and approved by the DAIDS PRO, and sites will receive an Amendment Registration Notification when the DAIDS PRO receives a complete registration packet. A copy of the Amendment Registration Notification should be retained in the site's regulatory files.

For additional information on the protocol registration process and specific documents required for initial and amendment registrations, refer to the current version of the DAIDS Protocol Registration Manual.

Protocol activation is required prior to enrolling participants into the study. The Network Coordinating Center will provide notification of activation.

Once a candidate for study entry has been identified, details will be carefully discussed with the participant. The participant will be asked to read and sign the approved protocol consent form.

For participants from whom a signed informed consent has been obtained, an ACTG Screening Checklist must be entered through the Data Management Center (DMC) Subject Enrollment System.

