4.5.2 Registration/Randomization

For participants from whom informed consent has been obtained, but who are deemed ineligible or who do not enroll into the initial protocol step, an ACTG Screening Failure Results form must be completed and keyed into the database.

Patients who are eligible for participation in the study based on screening results will be registered to the protocol at the time of enrollment.

During Stage 1, Group 1 participants who meet Step 2 entry criteria will be randomized 1:1:1 to one of three doses of INH (5, 10, or 15 mg/kg). Group 1 participants who do not meet Step 2 entry criteria, as well as Group 2 and 3 participants will be enrolled in Step 1, but will not receive study drug. They will be discontinued from the study after their Step 1, Day 0 visit and referred for standard local TB treatment.

During Stage 2, Group 1 participants who meet Step 2 entry criteria will be randomized as during Stage 1. Group 2 participants who meet Step 2 entry criteria will be registered and assigned to receive 5 mg/kg study drug daily.

Group 3 participants who meet Step 2 entry criteria will be randomized 1:1 to receive 15 mg/kg or 20 mg/kg study drug daily. Group 1, 2, or 3 participants who do not meet Step 2 entry criteria will be enrolled in Step 1, but will not receive study drug. They will be discontinued from the study after their Step 1 Day 0 visit and referred for standard local TB treatment.

During Stage 2, enrollment of Group 2 participants will proceed so that, on average, for every two Group 1 participants enrolled in Step 2 per month, one Group 2 participant will be enrolled. The enrollment for Group 2 will be controlled by setting a recruitment limit, and it will be manually adjusted by the data manager and statisticians routinely (e.g., every month or twice per month).

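### Section 3.0 bars people previously treated for MDR-TB, but the Step 2 entry criteria in Section 4 do not carry that exclusion

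*Protocol*

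**What the plan says.** Protocol Section 3.0 has a paragraph on protecting staff and participants. After describing ward separation, masks and negative-pressure ventilation, it names two kinds of people to be kept out. The first is "persons with a previous known exposure to XDR-TB". The second is "those who have been treated previously for MDR-TB, and thus have a higher risk of XDR-TB, will not be included in this study". The sentence gives its reason and leaves no discretion.

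The entry criteria in Protocol Section 4 read differently:

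- **4.4.3** excludes "Known exposure to a person diagnosed with XDR-TB or known personal diagnosis of XDR-TB in the past". It does not mention treatment for MDR-TB.
- **4.4.2**, both in the protocol and as revised by the clarification memo on washout, excludes "Receipt of more than 7 cumulative days of second-line anti-TB drugs" (and certain other antibiotics), counted only "within the 14 days prior to Step 1 screening sputum collection".
- **4.4.8** excludes any condition, including one found in the medical history, "which, in the opinion of the investigator, would interfere with participation in the study".

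The population line in the schema admits retreatment cases, and criterion 4.1.1 admits recurrent disease. Section 4.5.2 then states that "Group 3 participants who meet Step 2 entry criteria will be randomized 1:1 to receive 15 mg/kg or 20 mg/kg study drug daily". Section 4.5.1 adds that, after consent, "an ACTG Screening Checklist must be entered through the Data Management Center (DMC) Subject Enrollment System". The content of that checklist is not among the documents.

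**The concern.** One sentence in the design section makes two promises, and only one of them became an entry criterion. Sites screen against the numbered list in Section 4, and Section 4.5.2 bases randomization on that list. A site working from it could admit a person whom Section 3.0 excludes because of a higher risk of XDR-TB.

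What is at stake is infection control. A Step 2 participant must be willing to stay in hospital for at least 9 consecutive days (4.3.8). If the current strain is MDR, that person would be housed with other MDR-TB participants, because the ward separation in Section 3.0 is between MDR-TB on one side and drug-sensitive or INH-monoresistant TB on the other.

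Section 3.0 speaks of the study as a whole, and Step 1 has no exclusion criteria at all. Step 1-only participants need not be hospitalized, however, so the practical consequence falls mainly on Step 2.

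**Working it through.** This is a check of consistency between sections. There is no planned figure to reproduce.

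**Step 1. Look for the Section 3.0 rule in the criteria.** I compared the sentence with every item in Protocol 4.1 to 4.4 and with both Version 3.0 clarification memos.

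- 4.1 (Step 1 inclusion): smear-positive new or recurrent TB, age, genotype and consent. No limit on earlier MDR-TB treatment.
- 4.2 (Step 1 exclusion): none.
- 4.3 (Step 2 inclusion): group, weight, laboratory values, HIV status and CD4+ count, pregnancy and contraception, hospital stay, sputum volume. No treatment history.
- 4.4.1: recent INH only.
- 4.4.2: second-line drugs and certain antibiotics, within a short window (Step 2 below).
- 4.4.3: XDR-TB exposure or past XDR-TB only.
- 4.4.4 to 4.4.7: breastfeeding, INH allergy, general condition, neurological conditions.
- 4.4.8: could reach this history, but only if the investigator thinks it would interfere with participation.
- Memos: one revises the 4.4.2 washout; the other covers accrual, the web address and the CD4+ laboratory. Neither adds the exclusion.

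No item names previous MDR-TB treatment. One overlaps through a short window (4.4.2) and one is discretionary (4.4.8).

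**Step 2. What 4.4.2 can catch.** Take a daily second-line course whose last dose was *g* days before the Step 1 screening sputum (*g* of 1 or more). On the plain reading, the window is days 1 to 14 before that sputum. The days counted are max(0, 15 − *g*), and the person is excluded only if the count exceeds 7.

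- *g* = 7: 15 − 7 = 8 days, excluded.
- *g* = 8: 15 − 8 = 7 days, not excluded.
- *g* = 14: 15 − 14 = 1 day, not excluded.
- *g* = 15 or more: 0 days, not excluded.

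A different convention for the window's edge would move the boundary by a day. It would not change the result for a course that ended well before screening, which contributes 0 days.

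**Step 3. Follow one person through.** Take someone with recurrent smear-positive TB and a *katG* mutation who finished an MDR-TB course a year ago, with no known XDR-TB exposure or diagnosis.

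- Section 3.0: not to be included.
- 4.1.1 and 4.1.3: eligible for Step 1, Group 3.
- 4.4.2: 0 days against a limit of 7, passes.
- 4.4.3: passes.
- 4.4.8: passes unless the investigator decides otherwise.
- 4.5.2: if the remaining criteria are met, randomized to 15 or 20 mg/kg.

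The two sections give opposite answers for the same person.

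**Step 4. Does another check use XDR-TB status?** MTBDRsl testing for fluoroquinolone and injectable resistance is scheduled at Step 2 Day 0 for MDR-TB participants (Table 6.1-2). Its result feeds exploratory endpoint 9.2.3.3. No criterion in 4.3 or 4.4 uses the result, and Section 8.1 does not list it as a reason to discontinue.

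**Step 5. Size.** The Version 3.0 target for Group 3 Step 2 is 20 participants (2 cohorts × 10). The documents give no share with prior MDR-TB treatment, so the number affected cannot be computed.

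**The case against.** The strongest reply is that Section 3.0 is operative protocol text. It is worded as a prohibition, so admitting such a person would breach the protocol whether or not Section 4 repeats the rule. That stands. A reader might infer that the safeguard goes unapplied in practice. The documents do not show this, because the Screening Checklist content is not available. What they show is a rule stated in one section and absent from the list that governs randomization.

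It can also be said that other protections exist. Ward separation, N95 masks and negative-pressure wards apply regardless. Criterion 4.4.3 bars known past XDR-TB, 4.4.8 reaches medical history, and MTBDRsl is run on MDR-TB participants. Section 8.1 also lets the investigator withdraw a participant on judgement. These lower the risk and keep the point minor. None of them is the categorical bar that Section 3.0 describes.

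A reader might also infer from SAP Section 2.2 that the Section 3.0 sentence is a leftover, since an earlier letter of amendment relaxed 4.4.2 and removed a former 4.4.3. The SAP describes that change as concerning second-line drugs and antibiotics used before screening. Nothing shows that the removed item dealt with previous MDR-TB treatment, so this history cannot be used to presume that such people were meant to be eligible.

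Finally, the SAP's report sections already include baseline characteristics and ineligible participants. The Analysis Implementation Plan that details them is not among the documents, so the summary suggested below may already be planned.

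**Conclusion.** The inconsistency is real and sits in the current Version 3.0 text. Section 3.0 excludes people previously treated for MDR-TB, and the Step 2 criteria, including 4.4.2 as revised, do not. A retreatment case with a past MDR-TB course is barred by one section and meets the criteria used for randomization in the other.

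Severity is minor. The number affected is unknown and may be zero, and the Version 3.0 accrual concerned is 20 Group 3 Step 2 participants. The ward precautions remain in force.

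Two stronger readings are not supported. The documents do not show that anyone was wrongly enrolled. They also give no ground for claiming an effect on the EBA or MIC estimates.

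The conclusion assumes that Section 4 is the complete list of entry criteria and that the only Version 3.0 revisions to it are those in the two clarification memos supplied.

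**What to change.** By clarification memo, the route already used to revise 4.4.2, add *previous treatment for MDR-TB* to the Step 2 exclusions in Section 4.4. State that 7 days or less of second-line drugs, as allowed under 4.4.2, does not by itself count as previous treatment; otherwise the new line would conflict with 4.4.2. The criterion can be checked from the complete TB treatment history required by Table 6.3.5-1.

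Only if the sponsor confirms that such people were meant to be eligible should the Section 3.0 sentence be corrected instead. That has no accrual cost but withdraws a stated safeguard.

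If accrual has closed, report prior MDR-TB treatment by dosing cohort for the Group 3 Step 2 participants, using the TB Medication History CRF.

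The cost is one exclusion line and possibly slightly slower accrual of the 20 Group 3 Step 2 participants or, after closure, one summary row from data already collected.
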